9.2.3.2 Adverse events, serious adverse events

All AEs and SAEs will be coded to a “Lower Level Term (LLT)”, “Preferred Term (PT)”, “High Level term (HLT)”, “High Level Group Term (HLGT)” and associated primary “System Organ Class (SOC)” using the version of MedDRA (Medical Dictionary for Regulatory Activities) currently in effect at the sponsor at the time of database lock. MedDRA terms for hypersensitivity and injection site reactions will be included. The occurrence of AEs and SAEs is recorded from the time of signed informed consent until the end of the study.

9.2.3.3 Adverse event observation period

All reported AEs and SAEs are collected from the time of signed informed consent until the end of the study (defined as patient’s last visit planned per protocol or the resolution/stabilization of all SAE and adverse events of special interest (AESIs). All events will be managed and reported in compliance with all applicable regulations, and included in the final clinical study report.

If an AE/SAE is ongoing and not resolved by the end of the study observation period and leads to subsequent death of the patient, it will be reported.

The AE observations will be classified per the observation periods of safety data as defined above into:

- **Pre-treatment AEs** are AEs that developed or worsened or became serious during the pretreatment period.
- **Treatment-emergent AEs (TEAEs)** are AEs that developed or worsened or became serious during the on-treatment period.
- **Post-treatment AEs** are AEs that developed or worsened or became serious during the post-treatment period.

9.2.3.4 Death observation periods

The death observations are per the observation periods defined above. In addition, after the post-treatment period, death related to IMP as well as death resulting from TEAE must be reported to the Sponsor.

- Death on-study: deaths occurring during the on-study observation period (defined as the time from the signed informed consent date up to the end of the study, ie, last protocol planned visit or the resolution/stabilization of all SAE),
- Death on-treatment: deaths occurring during the on-treatment period.

9.2.3.5 Laboratory safety variables

The clinical laboratory data consist of blood analysis done at Central Laboratory at screening only (including LFTs and creatinine) Clinical laboratory values will be analyzed after conversion into standard international units. International units will be used in all listings and tables. No listings will be provided during the study and laboratory data from local laboratory related to AEs will not be entered into data base.

9.2.3.6 Vital Signs

Vital signs include heart rate and systolic and diastolic blood pressure in sitting position.

9.2.3.7 Electrocardiogram variables

ECG is not done routinely in the protocol. It may be done at the discretion of the investigator when clinically indicated. This data is not routinely recorded in the e-CRF and if abnormal, should be recorded as an AE.

9.2.3.8 Injection site reactions, hypersensitivity reactions and immunogenicity

No immunogenicity assessment is planned as part of the protocol. Injection site and local reactions are recorded on a standard AE page with its complementary page.

9.3 OTHER ENDPOINTS

9.3.1 Patient reported outcomes

Patients will complete self-reported questionnaires at designated time points in the study:

The Diabetes Treatment Satisfaction Questionnaire Status Version (DTSQs) will be used to evaluate patient satisfaction with treatment and patient perception of blood glucose control over a several week period. The DTSQs is comprised of 8 questions which are answered on a Likert scale from 0 to 6. Responses to these questions would be summarized into the three domain scores of Total Treatment Satisfaction, Hyperglycemia Perception and Hypoglycemia Perception such that a higher score would be indicative of better satisfaction. Mean differences in scores between groups would be evaluated to understand the impact of treatment on patient satisfaction.

The Diabetes Treatment Satisfaction Questionnaire Change Version (DTSQc) will be used to measure change in treatment satisfaction at 12 months. Scores for DTSQc treatment satisfaction items range from -3 to +3, and the sum of the treatment satisfaction scores range from -18 to +18. Positive scores are indicative of increases in treatment satisfaction relative to baseline measures. Perceived hyperglycemia and hypoglycemia items have scores that range from -3 to +3 in the DTSQc, with higher scores indicating more frequent perceived hyperglycemia or hypoglycemia by the end of the study. To control for baseline scores, DTSQs will be used as a measure of treatment satisfaction at baseline.

Patients will also complete the Hypoglycemia Patient Questionnaire which will require them to report frequency of hypoglycemia experienced during the course of the study. Responses to questions 5 & 6 on the Hypoglycemia Patient Questionnaire will be used to assess the endpoint. A patient report of 1 or more episodes of either moderate or severe hypoglycemia since the last visit will be indicative of patient experience of hypoglycemia. The proportion of patients reporting 1 or more episodes of either moderate or severe hypoglycemia will be compared between treatment groups.

Patient and Physician reported Global Effectiveness Scale (GES): This measure, originally developed to assess the impact of treatment on asthma control, will be adapted for diabetes (GES). The GES assesses impact of treatment on a 5-point scale (excellent, good, moderate, poor, or worsening of condition). These assessments will be completed twice by patients at 6 and 12 months. Physicians will complete the GES twice for each patient they manage at 6 and 12 months. Proportion of patients reporting “excellent” or “good” on the GES will be compared between the two treatment groups at each of the time points.

9.3.2 Health utilization endpoints

- Mean number and proportion of patients with hospitalizations over a 6 month and 12 month period,
- Mean number and proportion of patients with emergency room visits over a 6 month and 12 month period,

- Mean number of provider office visits and proportion of patients with specialty visits over a 6 month and 12 month period
- Mean overall and diabetes-related costs at 6 months and 12 months.

9.4 FUTURE USE OF SAMPLES

Not applicable.

9.5 APPROPRIATENESS OF MEASUREMENTS

The primary efficacy analysis will test superiority of Toujeo compared to other commercially available insulin in achieving individualized HEDIS HbA1c targets at 6 months without documented symptomatic or severe hypoglycemia as the primary endpoint. The 180 day duration of study treatment is considered to be sufficient for achieving steady state conditions with the commercially available basal insulins after randomization since there is no switching of basal, enabling an adequate assessment of time-dependent changes in HbA1c and the concomitant risk of hypoglycemia.

HbA1c is accepted by regulatory agencies as primary endpoint to support a claim based on glycemic control.

HbA1c is assayed using a central laboratory at screening V1 (Week -1), V3 (Day 180), and V4 (Day 360) (see [Section 1.2](#)).

10 STUDY PROCEDURES

10.1 VISIT SCHEDULE

The visit schedule and procedures/assessments listed in the “Study Flow Chart” (Section 1.2) are not repeated in this section. The aim of this section is to provide details on how some of the procedures/assessments have to be performed.

This is an outpatient study and consists of a minimum of a screening visit followed by 3 on-site visits and without routinely scheduled other visits or phone-call visits. In this “real world trial” additional, optional on site visits and phone call visits for “standard of care” should be scheduled whenever considered necessary by the investigator and consistent with usual practice and local standards of care. These additional “standard of care visits” are for the routine care of the patient and are not part of the trial visit schedule. Some of these visits may be to monitor and support the progress of insulin titration according to Investigator discretion or may be related to other aspects of diabetes management or general medical care.

Retesting of HbA1c in central laboratory is allowed where the HbA1c measured in Central Laboratory is unexpectedly lower than 8% and not consistent with local laboratory done prior to screening.

If the patient has HbA1c outside of inclusion range, they may be rescreened if the HbA1c is greater than 11% since they would be expected to improve under their physicians care. HbA1c rescreening is not allowed where there is the potential for patients to allow their control to deteriorate.

Patients may be screen failed if they miss the window for randomization and can then be rescreened.

Patients to be rescreened are reviewed by Sponsor and approved on a case by case basis.

All on-site visits should take place in the morning. The patient needs to be in fasting conditions at on site visit, V1, screening visit, (Week-1) and also for V3 (Day 180, baseline), and V4 (Day 360), or at early discontinuation from IMP. Patient is required to come to the visit after a fasting period of at least 8 hours: during this time, only water or tea without sugar or sweetener and without milk is allowed. No coffee, no other beverages are allowed.

Visit window: from the screening visit, (V1, Week -1), V2 (Day 1) until the primary efficacy endpoint visit (Day 180), visits should occur within ± 30 days. End of treatment (Day 360) may occur within ± 30 days. If one visit date is changed, the next visit should occur according to the original schedule.

Patients in the US do not need to bring their used or unused pens to visits other than EOT visit as a log of insulin pens will not be used to assess compliance. Patients in Canada need to bring their used and unused pens to the site when IMP will be dispensed by the site and to the EOT visit.

For a complete list of procedures scheduled for each study visit please refer to the Study flowchart (Section 1.2). The aim of the sections of the “Visit Schedule” as well as “Assessment Methods” in (Section 9, Section 10.1) is to detail procedures to be performed.

Patients who stop treatment early should be seen as soon as possible for an early end of treatment visit when 180 day assessment is completed and an EOT page in the CRF.

All data in the trial visits are reviewed by the clinician at the site who is qualified in the management of type 2 diabetes and initiation of insulin treatment.

10.1.1 Screening Period

The duration of the screening period is up to 1 week from Visit 1 (Week –1) to V2 (Week 0) such that patients must be randomized within 1 week of screening.

Patients will be screened at Visit 1 after signature of the informed consent form. All laboratory tests measured at central laboratory needed for checking the exclusion criteria of the patients will be performed at V1. Patients who meet the inclusion criteria and who have no exclusion criteria as noted in, Section 7.1, will be randomized at V2 (Day 1).

The IVRS/IWRS will be contacted at V1 for notification of screening and for patient number allocation.

10.1.1.1 On-site Visit 1 (Week -1) Screening visit

The following procedures/assessments will be performed at the visit 1 (Week-1):

- Obtaining the informed consent:
 - The patient will receive verbal information concerning the aims and methods of the study, its constraints and risks and the study duration. Written information will be provided to the patient. Written informed consent must be signed by the patient and investigator prior to any investigations.
- IVRS/IWRS notified (allocation of patient number, registration of screening, collection of demographic information).
 - The patient number is composed of a 9-digit number containing the 3-digit country code, the 3-digit center code and the 3-digit patient chronological number (which is 001 for the first patient screened in a center, 002 for the second patient screened in the same center etc).
- Assessment of inclusion/exclusion criteria.
- Demographics (age, gender, and ethnic origin).
- Patient’s medical (including detailed cardiovascular) and surgical history.
- History of type 2 diabetes treatment including documentation of insulin treatment regimen, and microvascular complications (eye, kidney) and their treatments.

- Concomitant medication history.
- Prior medication history, particularly as it relates to diabetes medications.
- Physical examination including vital signs (SBP and DBP including in sitting position, heart rate).
- Body height and weight.
- Laboratory testing by central laboratory:
 - HbA1c and FPG,
 - Serum pregnancy test in women of child bearing potential,
 - Safety laboratory; serum creatinine and LFT (please refer to [Section 9.2.3.6](#)).
- Instruction on recording information related to hypoglycemia in e-diary or on paper back up form, instruction on recording routine SMPG recommended by site either in e-diary or a paper diary per usual site practice, and AE reporting, (report any events that may occur after signing informed consent).
- DTSQs ([Appendix D](#)), Hypoglycemia Patient Questionnaire ([Appendix H](#)), and PAM ([Appendix F](#)) are administered at the screening visit completed and collected at the site.

10.1.1.2 Baseline Visit 2 (Week 0, Day1) +/-7 days

Patients meeting all inclusion criteria and with no exclusion criteria at the end of the screening period (based on data collected at the screening visit V1 (Week -1) are eligible to be randomized and can participate in the study.

For the complete list of procedures scheduled for this visit, please refer to the study flowchart [Section 1.2](#)) and for detailed description of assessments.

At this visit, the patient does not need to be fasting.

During the visit;

- Concomitant medications are reviewed.
- Patient diaries, both paper and electronic, are reviewed for hypoglycemia and AE/SAE by the Investigator or Sub-Investigator who are qualified and familiar with the study and then entered into the e-CRF.
- Dispensation of Bluetooth enabled glucometer, e-diary, training materials and supplies
- Training is provided for use of glucometer and e-diary. IVRS is called to randomize the patient.
- Diet and lifestyle counseling is provided according to the routine custom of the practice.
- DTSQs and the Hypoglycemia patient questionnaire will be completed
- In the US, patients will be provided with a prescription for Toujeo or the control insulin and a “smart card” for obtaining the insulin at a commercial pharmacy.

- Training is provided by the site investigator or site staff regarding insulin pen use.
- A patient card, including emergency contact details and treatment arm will be provided to every patient who participates in the study.
- Patient will be invited to be enrolled into the Toujeo PSP for those patients randomized to Toujeo. Patients may also choose to participate in other PSP available to them. Data on enrollment in a PSP will be collected at this visit.
- Patients are provided glycemic targets and guidance on dose adjustment at the discretion of the Investigator and consistent with local practice guidelines and recorded in the clinical source documents. This information is not recorded in the e-CRF.
- IVRS/IWRS notified
- At Canadian sites, process of dispensing insulin is discussed and first insulin may be provided by site.

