8.3 BLINDING PROCEDURES

Toujeo SoloSTAR pen and the control drugs, Lantus SoloSTAR and Levemir FlexTouch are distinguishable and so this study is an open-label design. Despite the open label administration of the study insulin, the assessments of outcome, the HbA1c and FPG are determined in central laboratories blinded to the treatment received. The study team will review the data for the primary efficacy parameters and adverse events without treatment assignments.

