2 STATISTICAL AND ANALYTICAL PROCEDURES

2.1 ANALYSIS ENDPOINTS

2.1.1 Demographic and baseline characteristics

The efficacy baseline value is defined as the last available value obtained before and up to the date of randomization.

Baseline HbA1c will be obtained at screening visit within one week of study initiation. For all safety measures, the baseline value is defined as the last available value prior to the first injection of IMP.

Demographic characteristics

Demographic variables are,

- Age in years,
- Age groups (<65, ≥65 and <75, and ≥75 years),
- Gender (Male, Female),
- Race (Caucasian/white, Black, Asian/Oriental, American Indian or Alaska Native, Native Hawaiian or other Pacific Island, other), and,
- Ethnicity (Hispanic, non-Hispanic).

Medical or surgical history

Medical or surgical history include medical history or surgical history related to diabetes and other medical or surgical history collected at Screening.

Medical history or surgical history related to diabetes are pre-specified medical or surgical history related to diabetes.

Other medical or surgical history will be coded to “Lower Level Term (LLT)”, “Preferred Term (PT)”, “High Level term (HLT)”, “High Level Group Term (HLGT)” and associated primary “System Organ Class (SOC)” by the version of Medical Dictionary for Regulatory Activities (MedDRA) currently in effect at the sponsor at the time of database lock.

Disease characteristics at baseline

Specific disease history includes history of diabetes collected at Screening and HEDIS components.

Diabetes history includes,

- Duration of type 2 diabetes (date of diagnosis),
- Age at diagnosis of diabetes,
- Diabetes duration (years),

- Diabetic complications, (diabetic retinopathy, diabetic sensory or motor neuropathy, diabetic autonomic neuropathy, and diabetic nephropathy),
- Anti-diabetic non-insulinic drugs,
- Previous participation to a PSP, and,
- PAM.

Note: PAM as an assessment of patient engagement. PAM score is detailed in Appendix F of Achieve Control protocol (1).

Vital signs

Vital signs at baseline are,

- Weight in kilograms,
- Weight group (<50, ≥50 and <100, and ≥100 kg),
- Height in centimeter,
- Body mass index (BMI) in kg/m²,
- Category of BMI (<25, [25-30], [30-40] and ≥40 kg/m²),
- Blood pressures, and,
- Heart rate.

Other baseline characteristics

Other baseline characteristics include,

- Randomization strata Individualized HbA1c target (<8%/<7%) from IVRS and electronic CRF (e-CRF) data,

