2.1.7.1 Diabetes Treatment Satisfaction Questionnaire Status Version

The DTSQs is a validated questionnaire to assess patient satisfaction with treatment and patient perception of BG control (3). The DTSQs will be used to evaluate patient satisfaction with treatment and patient perception of BG control over a several week period. The DTSQs is comprised of 8 questions which are answered on a Likert scale from 0 to 6. Responses to these questions would be summarized into the three domain scores of Total Treatment Satisfaction (Questions 1, 4-8), Hyperglycemia Perception (Question 2) and Hypoglycemia Perception (Questions 3) such that a higher score would be indicative of better satisfaction. Mean differences in scores between groups would be evaluated to understand the impact of treatment on patient satisfaction. DTSQs will be evaluated at Screening, Day 1, 6 months and 12 months in this study.

The total treatment satisfaction score and the 2 other scores are determined by computing the mean of item responses:

- Total treatment satisfaction score: sum of Items 1, 4, 5, 6, 7 and 8, ranging from 0 (no satisfaction) to 36 (high satisfaction),
- Perceived frequency of hyperglycemia score: Item 2, ranging from 0 (none of the time) to 6 (most of time),
- Perceived frequency of hypoglycemia score: Item 3, ranging from 0 (none of the time) to 6 (most of time).

The DTSQs endpoints are:

- Average scores on total treatment satisfaction from DTSQs at 6 months and 12 months,
- Average scores on hyperglycemia perception from DTSQs at 6 months and 12 months; and,
- Average scores on hypoglycemia perception from DTSQs at 6 months and 12 months.

Additionally, on these 3 scores (total treatment satisfaction, hyperglycemia perception and hypoglycemia perception), evaluation will be performed on:

- Change from baseline to 6 months,
- Change from baseline to 12 months,
- Change between 6 and 12 months.

Additional endpoints are:

- Percentage of patient responders on total treatment satisfaction score, defined as patients presenting a change from baseline to respectively Month 6 and Month 12 of at least the distribution-based minimal clinically important difference (MCID) value ([Section 2.5.1](#)).
- Percentage of patient responders on perceived frequency of hyperglycemia score, defined as patients presenting a change from baseline to respectively Month 6 and Month 12 of at least the standard MCID value ([Section 2.5.1](#)).

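### Nothing requires the Day 1 DTSQs before the open-label randomization call, and the SAP's date-based baseline rule, if applied to it, cannot exclude a score given after the patient knows the arm

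*Protocol*

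**What the plan says.** The insulin pens "are distinguishable and so this study is an open-label design" (Protocol 8.3), so the arm can be known from the moment of allocation.

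The Visit 2 list (Protocol 10.1.1.2) states in its fourth item that "IVRS is called to randomize the patient". The sixth item is "DTSQs and the Hypoglycemia patient questionnaire will be completed". The arm-specific prescription, the pen training, the patient card naming the arm and the Toujeo support-program invitation come later in the list.

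The DTSQs is also given at screening (Protocol 10.1.1.1). The SAP confirms both pre-treatment time points: "DTSQs will be evaluated at Screening, Day 1, 6 months and 12 months in this study" (SAP 2.1.7.1). It does not say which of the two is the baseline.

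The general efficacy rule is: "The efficacy baseline value is defined as the last available value obtained before and up to the date of randomization" (SAP 2.1.1). For patients randomized and not treated, SAP 2.1.3 instead uses the date and time of randomization.

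**The concern.** Treatment satisfaction and perceived frequency of hypoglycemia are subjective. A patient who has just learned which insulin was allocated may answer differently from one who has not. Randomization cannot balance a shift that arises after allocation.

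If such a score serves as baseline, part of any reaction to the allocation is subtracted from the later change. Patient-reported outcomes are a stated secondary objective (Protocol 5.2), and the protocol's rationale presents greater patient satisfaction as part of what interests payers (Protocol 4). A screening score, taken before allocation, is scheduled for every patient, but the date-based rule would pass over it.

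**Working it through.** No figure in the plan bears on this point, so the check is of the text, followed by short algebra.

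**1. Does the plan fix the order?** No.
- The Visit 2 list puts the questionnaires after the call but states no sequence.
- In the flow chart (Protocol 1.2) the questionnaire rows stand above the randomization row, and the chart states no sequence either.
- No section requires the questionnaires before the call, and none says that they follow it.

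**2. Which score does each SAP baseline rule select?** Take a patient with a screening DTSQs and a Day 1 DTSQs, randomized on Day 1.

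| SAP rule | Day 1 score given before the call | Day 1 score given after the call |
|---|---|---|
| Efficacy, by date (2.1.1) | Day 1 | Day 1 |
| Randomized and not treated, by date and time (2.1.3) | Day 1 | Screening |
| Laboratory efficacy (2.4.4) | HbA1c and FPG only | HbA1c and FPG only |

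The efficacy rule reaches the DTSQs only by inference. The link is SAP 2.4.7, which analyzes the scores in the manner of the continuous efficacy variables. The safety rule in SAP 2.1.1 (last value before the first injection) would normally give Day 1 too, but these questionnaires are not listed as safety endpoints.

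**3. What would a shift do?** Let F be the mean follow-up score, B the mean baseline score without the effect of knowing the arm, and d the mean shift in the Toujeo arm's Day 1 score relative to the comparator's. T and C denote the arms.

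- Observed difference in change = [F_T - (B_T + d)] - [F_C - B_C] = (true difference in change) - d. The bias is -d.
- In a model that adjusts for baseline DTSQs with slope b, the bias in the treatment effect is -b × d.
- In a model of the follow-up score without baseline DTSQs, the bias is 0.

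**4. Which planned analyses are exposed?**
- Change from baseline to 6 and to 12 months on three scores (SAP 2.1.7.1), with cumulative distribution plots (2.4.7): exposed, bias -d in the unadjusted difference.
- MCID responders (2.1.7.1, 2.5.1): exposed, because responder status depends on each patient's change.
- Change-based effect sizes (2.5.1): exposed in the numerator. The pooled SD is a weighted average of the arms' SDs, so a uniform shift within one arm leaves it unchanged.
- Consistency of DTSQs change with DTSQc (2.4.7): exposed.
- ANCOVA on the 6- and 12-month scores (2.4.7): not exposed. The listed covariates are HbA1c target, SU use, GLP-1 RA use and baseline HbA1c. SAP 2.1.7.2 says that DTSQs will serve as the baseline control for DTSQc. If that means adding it as a covariate, the -b × d result applies there.
- Post-baseline Hypoglycemia Patient Questionnaire comparison (2.1.7.3, 2.4.7): not exposed. No change analysis is planned and the baseline answer is not a covariate. Only the descriptive baseline proportion could be touched.
- Primary endpoint: not exposed.

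**The case against.** A reader might infer from the list that the satisfaction baseline is in fact taken with knowledge of the arm. The documents do not support that. The Visit 2 list cannot be read as strict chronology: its second item says "Patient diaries, both paper and electronic, are reviewed for hypoglycemia and AE/SAE", while the e-diary is only handed out in the third, "Dispensation of Bluetooth enabled glucometer, e-diary, training materials and supplies". A further IVRS notification appears near the end. A site could follow the protocol fully and give the questionnaires first.

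It can also be said that the SAP never expressly assigns the efficacy baseline rule to patient-reported outcomes, that the modeled score comparison does not use baseline DTSQs, and that secondary endpoints are declared exploratory and descriptive (Protocol 9.2.1, SAP 2.4.4.3).

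All of this stands, and it limits the point. It does not remove it. If the list sets no order, sites may use either order, and a rule that looks only at the date cannot tell the two apart. If the efficacy rule does not apply, the SAP has two pre-treatment scores and no rule for choosing between them.

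**Conclusion.** The point holds as a gap in the protocol and SAP taken together: the order of questionnaire and randomization call is left open, and the only general efficacy baseline rule would accept a score given after allocation. It is more than a missing detail, because following the list and the date rule as written can put such a score into several planned DTSQs analyses. It is a secondary matter, limited to those analyses.

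The bias in the unadjusted difference in change is -d. The documents give no value for d and no evidence that it differs from zero. Two assumptions carry the conclusion: that the efficacy baseline rule is applied to the DTSQs, and that at least some patients complete it after learning the arm.

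A reader might try to size the problem against sampling error. With an assumed SD of 5 to 8 points on the 0-36 scale and 1662 per arm, SE = SD × √(2/1662) = 0.17 to 0.28, and 1.96 × SE = 0.34 to 0.54 points. This shows only that a trial of this size has small standard errors. The SD is not in the documents, the formula is for a difference in means at one time point rather than in change, and it assumes that every patient contributes. It is not evidence of bias.

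**What to change.** 1. **Protocol 10.1.1.2:** place the DTSQs before the IVRS randomization call and say so explicitly. Move the Hypoglycemia Patient Questionnaire with it for consistency.
2. **SAP 2.1.7:** define the baseline for patient-reported outcomes as the last score before the date and time of randomization. Use the screening score when the Day 1 score was completed after the call, or when its timing relative to the call is not recorded.

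The SAP change matters more. Protocol 6.3 shows that enrollment was already under way, so reordering the list helps only patients not yet randomized, while the baseline rule covers everyone. Protocol 10.2.1 names dates and times of assessments among the source data, but the documents do not say whether the questionnaire's completion time reaches the database, hence the fallback.

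The cost is a reordered list and a short addition to the SAP, with no new data collection. For some patients the baseline is about one week older. A patient with no screening score and no Day 1 score known to precede the call would have no baseline for the change analyses.
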